4.2. Measures to minimise bias

This is a double-blind, placebo-controlled study.

The appearance and form of S95011 vials and placebo vials as well as the solutions to be administered will be similar, in order to protect the blinding with regard to the patients and the investigators.

Patients will be randomised to S95011 or placebo in an overall 2:1 ratio in order to minimise exposure to placebo and to gather more data on S95011. The randomisation will be non-adaptive, stratified by baseline intake of oral corticosteroids (yes/no) and baseline intake of antimalarials (e.g.: chloroquine, hydroxychloroquine, quinacrine) (yes/no).

Treatment randomisations and allocations will be centralized by Interactive Web Response System (IWRS). The structure responsible for designing and constructing the randomisation lists in blind will be the biostatistics department of I.R.I.S.

The questionnaires and patient's NRS will be administered to the patient with an electronic patient outcome (e-COA) in the local language. The same electronic device will be provided to each study patient. Data will be entered by the patient. The aim of this technology is to enhance quality of patient reported outcomes by reducing missing data and improving completion of the questionnaires.

Stability of the corticosteroids and disease background treatment(s) will be required during a pre- specified period before screening and during the study.

ESSDAI score will be completed by a trained investigator. The training will be performed before the inclusion of any patient in the site.

Over the course of the study, the ESSDAI will be completed by the same trained investigator for a given patient(sofar as possible).

A central laboratory will be used for the laboratory assessments (Serum haematology and biochemistry, coagulation tests, immune and auto antibodies panels, lymphocytes subsets...) in order to centralize and harmonize the data.

The determination of the drug concentration, of IL-7 and of receptor occupancy will be analysed by a central bioanalytical laboratory. The randomisation list will be sent to the bioanalytical lab in order to select the samples to be analysed.

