Missing data (not linked to intercurrent events) will be imputed according to the MAR assumption with a multiple imputation by treatment group.

The hypotheses to be tested are:

Let μ_0 and μ_1 be the population means of the change from baseline in ESSDAI score at W13 (primary endpoint) under placebo and S95011, respectively. The statistical hypotheses that will be tested are:

$$H_0: \mu_0 \geq \mu_1 \text{ (S95011 is not superior to placebo)}$$

versus

$$H_1: \mu_0 < \mu_1 \text{ (S95011 is superior to placebo)}$$

The type I error of the statistical tests will be set at 10% for unilateral situation, which is consistent with the objective of demonstrating the superiority versus placebo.

The following elements will be provided in a summary table:

- Estimate (standard error) of the difference between adjusted treatment group means.
- Two-sided 80% CI of the estimate
- Two-sided 95% CI of the estimate.
- One-sided p-value

10.1.2.4.1.2. Sensitivity analyses

In order to assess the sensitivity to the missing at random (MAR) assumption, values post the following IEs:

- change or initiation of unauthorised medication,
- study drug discontinuation for major worsening of primary Sjögren's syndrome or AE related to study drug,

will not be taken into account and will be imputed according to the missing not at random (MNAR) assumption. The values of outcome will be imputed using a reference based multiple imputation ("copy increments in placebo" approach) for S95011 group and using multiple imputation for the placebo group. This approach assumes that patients from S95011 will exhibit an evolution of the disease similar to patients in the placebo group but starting from the benefit already obtained (Carpenter *et al*, 2013). The imputed value will reflect the fact that these IEs are considered a moderately bad outcome. The others IEs and missing data will be handled as in the primary analysis.

10.1.2.4.1.3. Supplementary analyses

Responders ESSDAI at W13 defined as patients having improvement from baseline in ESSDAI total score of at least:

- 3 points
- 5 points
- 7 points

will be analysed separately using a logistic regression model including the fixed, categorical effect of treatment and randomisation stratification factors (*rando_factor*) as well as the continuous fixed covariate of baseline value. The handling of IEs and missing data will be the same as the primary and sensitivity analysis.

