10.1.2.4.3. Additional estimands based on ESSDAI and ESSPRI

Treatment policy estimands

Treatment policy estimands are defined in order to assess the treatment effect on the clinical disease activity (ESSDAI) and also on the symptoms reported by the patients (ESSPRI) regardless of whether or not the IE occurs.

The attributes of the additional estimands are defined as follow:

- Treatment: S95011 or placebo, regardless of whether or not the IE occurs
- Population: RS
- Variable 1: change in ESSDAI total score from baseline to W13
- Variable 2: change in ESSPRI total score from baseline to W13
- Summary measure: difference in means between treatments.
- Intercurrent events: The occurrence of IEs (see list in primary estimand) is irrelevant in defining the treatment effect of interest. All observed values will be used regardless of occurrence of an IE.

Main and supplementary analyses are the same as for the primary estimand.

Other estimand

This estimand of interest is the effect of the randomised treatments on the composite response to treatment taking into account a double dimension - clinical disease activity from ESSDAI and symptoms reported by the patients from ESSPRI - in all patients assuming non-occurrence of IEs. The motivation for this choice is the same as the primary estimand.

The attributes of this estimand are defined as follows:

- Treatment: S95011 or placebo.
- Population: all randomised patients (RS).
- Variable: Number of responders defined as patients with ≥ 3 points of improvement in ESSDAI and with ≥ 1 point of improvement in ESSPRI from baseline at W013.
- Summary measure: difference in proportion between treatments.

- Intercurrent events (IE):
 - change or initiation of unauthorised medication
 - study drug discontinuation for major worsening of primary Sjögren’s syndrome or AE related to study drug
 - study drug discontinuation for other reasons (non-medical reason, AE not-related...)
 - unexpected others events having an major impact on the pharmacologic effect evaluation (They will be defined at the latest in the final version of the SAP)

S95011 will be compared to placebo on the responders in the RS using a logistic regression model including the fixed, categorical effect of treatment and randomisation stratification factors (*rando_factor*) as well as the continuous fixed covariate of baseline value. The handling of IEs and missing data will be the same as the primary analysis of the primary estimand.

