10.2. Determination of sample size

The following efficacy criteria are defined:

- a statistically significant reduction in ESSDAI at Week 13 in the S95011 group compared to placebo, at the one-sided 10% significance level
- an estimated mean reduction in ESSDAI in the S95011 group to be 3 points or greater than placebo. The decrease of 3 points was chosen because it is considered as clinically minimal relevant (Seror *et al*, 2016).

Targeted sample size

With 45 patients in the primary analysis of the primary estimand (30 in the S95011 group and 15 in the placebo group), the study would have around 5% chance of having a false-positive result, *i.e.*, of meeting both the efficacy criteria when the true difference between S95011 and placebo is zero. Additionally, the chances of meeting both the efficacy criteria remain below 14% for true differences between S95011 and placebo of less than 1 point.

The study would have approximately 70% chance of meeting both the efficacy criteria, when the true difference between S95011 and placebo is 4 points. In case the true difference between S95011 and placebo is only 3 points, the study would have approximately 50% chance of meeting both the efficacy criteria. These calculations assume that the primary efficacy endpoint, change from baseline in ESSDAI, follows a normal distribution with a standard deviation of 6. This estimate of the standard deviation is based on some clinical studies (Fisher *et al*, 2020; UCB5857; RO5459072) in patients with primary Sjögren's syndrome in which the observed standard deviation ranged from around 4 to 6.

Blinded standard deviation reassessment

The similar operational characteristics (false-positive and right-positive rates) are obtained with 20 patients in S95011 group and 10 patients in placebo group under assumption of an overall standard deviation of primary efficacy endpoint of 5. So, only if the recruitment is much longer than expected, when 30 patients will have completed the 13-week treatment period, the overall standard deviation of the primary endpoint on non-comparative data could be calculated. If the value is less or equal to 5, the sponsor could stop the patient recruitment, considering that the number of patients is sufficient to meet both efficacy criteria. This potential adaptation has very little or no impact on the probability of having a false-positive result (Kieser, 2003).

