4.3.1.3. Supplementary analyses

Supplementary analysis will be done on RS.

Definition: the efficacy endpoint is defined as the proportion of responders in ESSDAI total score at W013.

Supplementary analysis: to assess the efficacy of S95011 (750 mg) as compared to Placebo on proportion of responders in ESSDAI after a 13-weeks treatment. Responders in ESSDAI at W013 defined as patients having improvement from baseline in ESSDAI total score of at least:

- 3 points
- 5 points
- 7 points

will be analysed separately using a logistic regression model including the fixed, categorical effect of treatment and randomization stratification factors (*rando_factor*) as well as the continuous fixed covariate of baseline value.

LOGISTIC REGRESSION MODEL: responder = baseline rando_factors treatment [2]

The assumptions underlying the model, as for instance, independence of errors, linearity in the logit for continuous variables, absence of multicollinearity, and lack of strongly influential outliers will be checked.

If the model is not running due to too few patients in the stratas, the model mentioned above will be modified. Thus, the two stratification factors in the model will be replaced by the following composite factor: baseline intake of oral corticosteroids or antimalarial or both (yes/no). If the model is still not running with the stratification factor in two classes, then the stratification factor will not be considered.

Missing data/intercurrent events handling: the handling of IEs and missing data will be the same as the primary and sensitivity analysis. Thus, imputation will be done on the change and then the imputed change values will be turned into responder/non-responder.

Multiplicity handling: there is no multiplicity issue.

Statistical elements: Finally, the following elements will be provided in a summary table:

- Estimate (standard error) of the difference between adjusted treatment arm proportions.
- Two-sided 80% CI of the estimate.
- Two-sided 95% CI of the estimate.
- One-sided p-value.

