7.3.2. Logistic Model

Another model that will be used for this study for the responder analysis is the Logistic Model studying treatment effect with baseline and randomisation stratification factors (baseline intake of oral corticosteroids (yes/no) and baseline intake of antimalarial (yes/no)) variable as covariates. The randomisation stratification factors will be considered in a unique variable with four modalities (“Nothing”, “oral corticosteroids”, “antimalarial” and “oral corticosteroids and antimalarial”).

Logistic regression is one of the generalized linear models with a logit link to model a binary dependent variable. Under logit setting, we can model our response as below:

$$\log \frac{E[P(Y = 1)]}{1 - E[P(Y = 1)]} = \beta_0 + \beta_1 * I_{treatment} + \beta_2 * X_2 + \beta_3 * X_3 + \beta_4 * X_4$$

Let L_p and L_T be the linear predictor for placebo and treatment, respectively

$$L_T = \beta_0 + \beta_1 + \beta_{T2} * X_2 + \beta_{T3} * X_3 + \beta_{T4} * X_4$$

$$L_p = \beta_0 + \beta_{p2} * X_2 + \beta_{p3} * X_3 + \beta_{p4} * X_4$$

Estimate:

The difference between two rates can be considered as a function of β :

$$E[P(Y = 1|T)] - E[P(Y = 1|P)] = h(\beta) = \frac{1}{1 + \exp(-L_T)} - \frac{1}{1 + \exp(-L_P)}$$

So the difference in percentages of responders between Treatment and Placebo will be given by:

$$\text{diff}_{\%}(T - P) = \frac{\exp(L_T)}{1 + \exp(L_T)} - \frac{\exp(L_P)}{1 + \exp(L_P)}$$

Then the standard error for rate difference can be derived by Delta method.

$$\sqrt{n}(\hat{\beta} - \beta) \sim N(0, \Sigma)$$

The delta method will be applied using the NLMIXED procedure of SAS on the results from the GENMOD procedure (Ke, 2022).

```
ods output AdditionalEstimates=output_nlmixed;
proc nlmixed data=data_analyse alpha=risk_alpha;
p = logistic(Intercept + b1*(class=1) + b2*(class=2) + b3*(class=3) + b4*baseline +
b5*(treatment=1));
model response ~ binary(p);
by _Imputation_;
estimate 'T-P' logistic(Intercept + 0.25*b1 + 0.25*b2 + 0.25*b3 + 12.146*b4 + b5) -
logistic(Intercept + 0.25*b1 + 0.25*b2 + 0.25*b3 + 12.146*b4);
run;
```

The values in green above are an example and will be replaced by coefficients extracted from proc genmod.

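### The responder analyses have no rule for a placebo arm without responders: the delta-method standard error then fails, and the real one-sided level at a nominal 10% is left undetermined

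*Protocol*

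**What the plan says.** Protocol 10.1.2.4.1.3 states that patients improving by at least 3, 5 or 7 ESSDAI points "will be analysed separately using a logistic regression model including the fixed, categorical effect of treatment and randomisation stratification factors", with baseline as covariate. For the ESSDAI/ESSPRI composite, Protocol 10.1.2.4.3 states that "S95011 will be compared to placebo on the responders in the RS using a logistic regression model". The protocol goes no further on method.

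The method is fixed in SAP 7.3.2. The logistic model is fitted with GENMOD, the risk difference is computed in NLMIXED, and "Then the standard error for rate difference can be derived by Delta method". SAP 4.3.1.3 reports that difference with its standard error, 80% and 95% confidence intervals and a one-sided p-value. SAP 4.3.2 to 4.3.5 use logistic models of the same type for ESSPRI responders, the composite, STAR and CRESS. The STAR and CRESS models contain strata and treatment but no baseline score.

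The only safeguard applies when a model does not run because strata hold too few patients. The four-class factor is then reduced to two classes, and after that: "If the model is still not running with the stratification factor in two classes, then the stratification factor will not be considered". Neither document names a penalised, score or exact method, or gives a rule for an arm with no responders. Neither gives an expected placebo responder rate.

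**The concern.** The delta-method variance of a fitted proportion is proportional to p(1−p). If no placebo patient responds, the fitted placebo rate goes to zero and its variance goes with it, so the interval for the difference reflects the S95011 arm only. Fifteen patients are too few to treat a rate as known. Merging or dropping strata does not help, because the separation is by treatment and remains when the strata have gone.

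A second gap compounds this. The SAP does not say whether separation counts as a model that is not running. One analyst might keep a four-class fit with diverging coefficients, and another might go down the fallback. The two routes err in opposite directions, so the reported intervals and p-values depend on an unwritten choice.

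**Working it through.** **Inputs.** 30 S95011 and 15 placebo patients, and a change in ESSDAI that "follows a normal distribution with a standard deviation of 6" (Protocol 10.2). Nominal level 10% one-sided (Protocol 10.1.2.4.1.1). Model and standard error from SAP 7.3.2.

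**The plan's own figures.** No operating characteristic is stated for the responder tests. The sizing of the primary endpoint reproduces: SE = 6·√(1/30+1/15) = 1.897. The binding cut-off is the larger of 3 and 1.2816·1.897 = 2.43, that is 3. Then 1−Φ((3−δ)/1.897) gives 5.7% at δ=0, 14.6% at 1, 50.0% at 3 and 70.1% at 4. The plan states around 5%, below 14% (for differences under 1), 50% and 70%.

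**How likely is 0/15?** Assume a normal change with SD 6 and zero mean placebo change. The responder rates are 1−Φ(7/6) = 12%, 1−Φ(5/6) = 20% and 1−Φ(3/6) = 31%. At the rounded 12% rate, P(0/15) = 0.88^15 = 15%. At 20% it is 3.5%, and at 30% it is 0.5%. With a mean change of −3 and SD 6, P(0/15) for 7 points falls to 1.3%. With SD 4 and mean 0 the rate is 4% and P(0/15) is 54%. The normal model also ignores the floor: a patient whose baseline ESSDAI is 6 cannot improve by 7.

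**What the formula does at 0/15 (treatment only).** The fitted placebo SE is 0.0001, whereas the exact one-sided 90% upper limit for 0/15 is 1−0.1^(1/15) = 14.2%.

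- 2/30 v 0/15: SE = √(0.0667·0.9333/30) = 0.0455, z = 1.46, p = 0.072. Pooled score: 2/45 = 0.0444, SE = √(0.0444·0.9556·0.1) = 0.0652, p = 0.15. Fisher: (30·29)/(45·44) = 0.44.
- 3/30 v 0/15: SE = 0.0548, z = 1.83, p = 0.034. Score 0.10, Fisher 0.29.

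With 1/15 the placebo SE is 0.064, so the near-zero variance belongs to 0/15 alone.

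**Level at a nominal one-sided 10%, equal true rates.** The treatment-only column is exact enumeration. The four-class and fallback columns are simulations of the baseline-adjusted model (3,000 trials per setting). Their ranges cover three assumed corticosteroid/antimalarial usage pairs (20/30%, 30/40%, 50/50%), with an assumed baseline distribution. The fallback is followed whenever a stratum has no responders or only responders. The Firth column is a penalised four-class fit with a delta-method difference (2,000 simulations).

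| True rate | Treatment only | Four-class kept | Fallback followed | Firth, four-class |
|---|---|---|---|---|
| 5% | 20.8% | 0.3–0.6% | 14.8–14.9% | 3.9% |
| 10% | 19.4% | 1.3–3.0% | 15.7–16.0% | 7.9% |
| 20% | 14.3% | 4.0–10.2% | 14.1–15.2% | 8.9% |
| 30% | 12.2% | 6.1–12.4% | 13.5–14.0% | 10.6% |
| 40% | 12.0% | 6.4–13.1% | 12.6–13.7% | 8.9% |

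The treatment-only maximum is 21.9%, at a rate of 6.5%. At 15% the fallback range is 15.8–16.5%. The four-class model is conservative at low rates because a stratum without responders inflates the standard error. A second simulation gave about 3% at 12%, 8% at 20% and 11% at 31% for the four-class model, about 14–16% once strata are dropped, and about 9–12% for Firth.

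**Where the excess arises (treatment only).** At a 5% rate, 20.7 of the 20.8 points come from 0/15; at 10%, 16.8 of 19.4. At 20%, 10.8 of 14.3 points come from non-zero placebo cells, but the total excess is then modest.

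**The case against.** The strongest defence is that the planned model, kept as written, does not over-reject where zero cells are likely: at 5–10% response rates its level is 0.3–3.0%. A reader might infer from the treatment-only figures that the responder tests run at twice their nominal level. The documents do not support that. The treatment-only model arises only for STAR and CRESS, after both fallback steps. Every other responder model also carries baseline.

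A reader might also infer that all responder endpoints are affected alike, or that any small number of placebo responders causes the failure. Neither is shown. No placebo rate can be derived from the documents for ESSPRI, the composite, STAR or CRESS, and CRESS gives points for a clinESSDAI below 5 and for an eye test that merely stays normal.

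Nor does the proof-of-concept decision rest on these analyses. The efficacy criteria in Protocol 10.2 and SAP 1.2 use the continuous ESSDAI change only. The statement that "The type I error of the statistical tests will be set at 10% for unilateral situation" directly follows the hypotheses on the primary means, and SAP 4.3.1.3 sets no decision rule for responders.

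All of this limits the scope. What stands is that following the SAP exactly can give misleading error bars in either direction, and the SAP does not say which route applies.

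**Conclusion.** The point holds as a defect of specification in supplementary and additional analyses. With 0/15 placebo responders the delta-method interval ignores the uncertainty of the placebo rate, and the stated fallback cannot repair it. The one-sided level is therefore not fixed by the plan: strongly conservative if the four-class model is kept at low response rates (roughly 0.3–4% at 5–12%), about 13–16% along the fallback, and at worst 22% for a treatment-only model. At 30–50% response rates the treatment-only excess is small (about 12%).

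The practical risk is concentrated in the 7-point ESSDAI cut-off and any other rare response. It rests on assumed placebo rates: with SD 4 to 6 and a mean placebo change of 0 to −4, the 7-point rate runs from 4% to 31%. The simulated levels also rest on assumed background-therapy use and baseline scores. Behaviour under the 100 imputations was not simulated and could change the levels.

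**What to change.** In SAP 7.3.2, and by reference in 4.3.1.3 and 4.3.2 to 4.3.5, fit all responder logistic models with Firth's penalised likelihood. Keep the planned covariates, and take the risk difference, its 80% and 95% intervals and the one-sided p-value from that fit in each imputed data set before combination.

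At minimum, add one sentence: *Separation, or an arm with no responders or only responders, triggers the Firth-penalised fit; the stratification factor is not dropped for this reason.*

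The cost is a small code change and slight shrinkage of the estimate. In the simulations the Firth fit ran between 3.9% and about 12%, so it is conservative for very rare responses and close to nominal otherwise. It should be checked once under the planned imputation. Replacing the models by a stratified Cochran–Mantel–Haenszel test with a Miettinen–Nurminen interval is not needed: it gives up the baseline covariate, strata with an empty arm contribute nothing, and score intervals do not pool directly over 100 imputations.

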10.1.2.4.2. Secondary estimand based on the ESSPRI

The secondary estimand of interest is the effect of the randomised treatments on symptoms reported by the patients in all patients assuming non-occurrence of IEs. The motivation for this choice is the same as the primary estimand.

Compared to the primary estimand, only the *variable* attribute is different and is defined as the change in ESSPRI total score from baseline to W13 (secondary efficacy endpoints).

The other attributes, main and sensitivity analyses are the same as for the primary estimand. In the same line as for the primary estimand, the supplementary analyses will be performed on the responders ESSPRI at W13 defined as patients having improvement from baseline in ESSPRI total score of at least:

- 1 point
- 2 points
- 3 points.

using the same model as for responders ESSDAI.

10.1.2.4.3. Additional estimands based on ESSDAI and ESSPRI

Treatment policy estimands

Treatment policy estimands are defined in order to assess the treatment effect on the clinical disease activity (ESSDAI) and also on the symptoms reported by the patients (ESSPRI) regardless of whether or not the IE occurs.

The attributes of the additional estimands are defined as follow:

- Treatment: S95011 or placebo, regardless of whether or not the IE occurs
- Population: RS
- Variable 1: change in ESSDAI total score from baseline to W13
- Variable 2: change in ESSPRI total score from baseline to W13
- Summary measure: difference in means between treatments.
- Intercurrent events: The occurrence of IEs (see list in primary estimand) is irrelevant in defining the treatment effect of interest. All observed values will be used regardless of occurrence of an IE.

Main and supplementary analyses are the same as for the primary estimand.

Other estimand

This estimand of interest is the effect of the randomised treatments on the composite response to treatment taking into account a double dimension - clinical disease activity from ESSDAI and symptoms reported by the patients from ESSPRI - in all patients assuming non-occurrence of IEs. The motivation for this choice is the same as the primary estimand.

The attributes of this estimand are defined as follows:

- Treatment: S95011 or placebo.
- Population: all randomised patients (RS).
- Variable: Number of responders defined as patients with ≥ 3 points of improvement in ESSDAI and with ≥ 1 point of improvement in ESSPRI from baseline at W013.
- Summary measure: difference in proportion between treatments.

- Intercurrent events (IE):
 - change or initiation of unauthorised medication
 - study drug discontinuation for major worsening of primary Sjögren’s syndrome or AE related to study drug
 - study drug discontinuation for other reasons (non-medical reason, AE not-related...)
 - unexpected others events having an major impact on the pharmacologic effect evaluation (They will be defined at the latest in the final version of the SAP)

S95011 will be compared to placebo on the responders in the RS using a logistic regression model including the fixed, categorical effect of treatment and randomisation stratification factors (*rando_factor*) as well as the continuous fixed covariate of baseline value. The handling of IEs and missing data will be the same as the primary analysis of the primary estimand.

